### 6.1. Adverse Events

Adverse Event (AE) is defined as any new untoward medical occurrence or worsening of a pre-existing medical condition in a subject administered a medicinal product in a clinical investigation and which does not necessarily have a causal relationship with this treatment. An AE can therefore be any unfavorable and unintended sign (including an abnormal laboratory finding, for example), symptom, or disease temporally associated with the use of a product (investigational or marketed), whether or not considered related to the product (investigational or marketed).

Treatment-emergent AEs: any adverse event starting on or after the first treatment dose.

AE Severity:

**CTCAE term (AE description) and grade:** The descriptions and grading scales found in the revised NCI Common Terminology Criteria for Adverse Events (CTCAE) Version 4.0 will be utilized for AE reporting. A copy of the CTCAE Version 4.0 can be downloaded from the CTEP web site (<http://ctep.cancer.gov>).

All appropriate treatment areas should have access to a copy of the CTEP CTCAE Version 4.0 (see Protocol Appendix E)

AE Attribution (Relationship)

The following categories and definitions of causal relationship or attribution to study drug should be used to assess Adverse Events:

- Definite: There is a reasonable causal relationship between the study drug and the event. The event responds to withdrawal of study drug (dechallenge) and recurs with rechallenge, if clinically feasible.
- Probable: There is a reasonable causal relationship between the study drug and the event. The event responds to dechallenge. Rechallenge is not required.
- Possible: There is a reasonable causal relationship between the study drug and the event. Dechallenge information is lacking or unclear.
- Unlikely: There is doubtful causal relationship between the study drug and the event.
- Unrelated: There is clearly not a causal relationship between the study drug and the event or there is a causal relationship between another drug, concurrent disease, or circumstances and the event.

Categories 'Definite', 'probable' and 'possible' are considered study drug related. Categories 'not likely' and 'not related' are considered not study drug-related.

The development of a new cancer is to be regarded as an AE. New cancers are those that are not the primary reason for administration of study treatment and have been identified after inclusion of the subject into the clinical study.

A **serious AE** is any untoward medical occurrence occurring after informed consent is granted or that at any dose:

- results in death,

- is life-threatening (defined as an event in which the study subjects was at risk of death at the time of the event; it does not refer to an event which hypothetically might have caused death if it were more severe),
- requires inpatient hospitalization or causes prolongation of existing hospitalization,
- results in persistent or significant disability/incapacity,
- is a congenital anomaly/birth defect,
- is an important medical event (defined as a medical event(s) that may not be immediately life-threatening or result in death or hospitalization but, based upon appropriate medical and scientific judgment, may jeopardize the subject or may require intervention (e.g., medical, surgical) to prevent one of the other serious outcomes listed in the definition above.) Examples of such events include, but are not limited to, intensive treatment in an emergency room or at home for allergic bronchospasm; blood dyscrasias or convulsions that do not result in hospitalization.

#### Second Primary Cancers:

New cancers are those that are not the primary reason for administration of study treatment and have been identified after inclusion of the subject into the clinical study.

All cases of new primary cancers that occur during or after the start of protocol treatment are to be reported to PrECOG within 30 days of diagnosis, regardless of relationship to protocol treatment. Secondary primary malignancies should also be reported as a SAE.

#### **6.2. Concomitant Medications**

Bone modifying medications taken during the study are to be recorded on eCRF .

## 7. GENERAL STATISTICAL CONSIDERATIONS

Statistical analysis and programming of tables and listings will be conducted by QDS, using SAS® Release 9.2 (SAS Institute Inc., Cary, North Carolina, USA). After the TFLs are approved as final, SAS programs used to perform statistical analyses and generate analysis datasets and TFLs will be archived in 2 formats (ASCII, and .PDF); the analysis SAS Datasets will be archived in XPT format created using SAS PROC XPORT.

The analyses described in this section are applicable for the planned TLFs listed in Appendix 1.

### 7.1. Methodology

Continuous data will be summarized with the following descriptive statistics: number of observations, mean, (n) standard deviation (StdDev), median, minimum (min), and maximum (max). Categorical data will be summarized with frequencies and percentages.

Listings will be presented by subject and all data will be presented. Tables will be presented by treatment arms and only data pertaining to the specific population being analyzed will be used.

### 7.2. Analysis Populations

The protocol defines the following analyses populations:

Evaluable for toxicity: All treated subjects (defined as subjects who receive at least one dose of fulvestrant or everolimus/placebo) are evaluable for toxicity from the time of their first treatment with fulvestrant and everolimus/placebo. All subjects are to be followed for 30 days for toxicity after the last dose of study therapy (fulvestrant and/or everolimus/placebo) or until recovery from all toxicity (to ≤ grade 1) attributed to study therapy, whichever is longer (or if >grade 1, event must be permanent and stable).

Evaluable for objective response: Subjects will be classified into two groups according to their measurable disease stratification level at randomization. Subjects with measurable disease (with or without bone only metastases) will have their responses classified according to the definitions stated in Protocol Section 6.1.2 and SAP Appendices 3 through 5. Subjects in this stratum who are unevaluable for objective response will be included in the denominator when calculating the response rate.

Evaluable for non-target disease response: Subjects who are stratified into the bone metastases only cohort at randomization will be considered evaluable for non-target disease. The response assessment is based on the presence, absence, or unequivocal progression of the lesions. Subjects who are free of new lesions and free of unequivocal progression will be considered to have clinical benefit.

Evaluable for efficacy: The primary efficacy analysis will be done including eligible, treated subjects.

Intent-to-treat (ITT) analysis population includes all subjects as randomized. Sensitivity analyses of efficacy will be done among all subjects as randomized (ITT population).

The next sections will indicate the required analysis population for the planned analyses. This is also documented in each TLF template.

### **7.3. Subject Disposition**

The following summary tables will be prepared to describe subjects' disposition and case status for all enrolled subjects:

#### **7.3.1. Accrual by Institution**

Number and percentage of subjects enrolled and ineligible will be summarized by study site overall. Number of randomized subjects, withdrawn before treatment, eligible and treated will be summarized by site and by randomized treatment arm. Percentages for ineligible will be based on all enrolled. Percentages for randomized subjects are based on all enrolled. Percentages for withdrawn before treatment, eligible and treated will be based on the number randomized within each treatment arm.

#### **7.3.2. Case Status**

Number and percentage of subjects enrolled and ineligible will be summarized overall. Number of randomized subjects, withdrawn before treatment, eligible and treated will be summarized by randomized treatment arm. Percentages for ineligible will be based on all enrolled. Percentages for randomized subjects are based on all enrolled. Percentages for withdrawn before treatment, eligible and treated will be based on the number randomized within each treatment arm.

Number and percentage of subjects who completed Induction phase, discontinued during induction phase, were unblinded during induction phase, continued in Continuation phase, completed study, and discontinued the study will be summarized by treatment arm and overall. Percentages are based on number of eligible and treated subjects.

Subject's reasons for discontinuation at the end of treatment will be summarized by the following categories: adverse events, death, progressive disease, symptomatic progression, physician decision, protocol non-compliance, withdrawal by subjects, study terminated by sponsor, or unknown. If there are still subjects on treatment at the time the clinical study report is prepared, an additional category "Remain on treatment" will be included. Percentages will be calculated based on number of eligible and treated subjects.

### **7.3.3. Reasons Subjects were Ineligible**

These will be summarized in a by subjects data listing including inclusion / exclusion criteria not met by subjects considered ineligible for the study

### **7.3.4. Reasons Subjects did not Start Treatment**

Per protocol, subjects are to start treatment within 7 days post randomization. Subjects who were randomized and discontinued study prior to starting treatment will be listed. This listing will include randomized subjects who discontinued prior to induction phase and do not have a corresponding record in EX domain or have only one record in EX domain indicating Fulvestrant or Everolimus/Placebo not administered. Reason for discontinuation will be based on End of Treatment CRF (DS domain).

### **7.3.5. Stratification Factors**

A summary of responses for the 3 stratification factors considered for randomization will be prepared by treatment arm and overall. The 3 factors are: performance status (1 or 0), measurable disease (yes or no), and prior chemotherapy (yes or no). This information will be based on IWR.

Since performance status is assessed again on Day 1 of Cycle 1, a cross-tabulation between performance status as reported and recorded in IWR and performance status as recorded on Day 1 Cycle 1 will be prepared (overall and by treatment group).

For both tables, percentages will be based on number of randomized subjects.

## **7.4. Subject Characteristics**

Demographic and baseline characteristics will be summarized overall and by treatment arm for randomized subjects. The following variables will be summarized:

- Age (years) as continuous variable
- Sex (female, male)
- Race categories
- Ethnicity categories
- Time since diagnosis (months) as continuous variable
- Number and percentage of subjects who developed locally recurrent disease
- Number and percentage of subjects who developed metastatic disease
- Time since recurrence / progression (months) as continuous variable

- Sites of recurrence of metastasis
- ER status
- PR status
- HER2 Neu and HER2Neu FISH results
- Prior anti-cancer therapies (Number of regimens)
- Prior bone-modifying medications (Number of regimens)

Time since diagnosis = (date of informed consent – date of diagnosis + 1)/30.4375.

Time since recurrence / progression = (date of informed consent – date of recurrence / progression + 1)/30.4375

Partial dates for date of diagnosis or for date of recurrence / progression will be imputed as follows:

- if the day is missing, it will be imputed it to be 15th of the month; for example, if date is recorded as JUL-1990, the imputed the date will be 15-JUL-1990;
- if the day and the month are missing, it will be imputed to 30-JUN; for example, if only 1976 is recorded, the imputed date will be 30-JUN-1976.

Percentages will be based on number randomized. Results will be summarized for all randomized subjects and for the Evaluable for Efficacy population (including eligible and treated subjects).

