3.1 Eligibility Criteria

Each of the criteria in the following section must be met in order for a patient to be considered eligible for this study.

PrECOG will not grant any exceptions or waivers to protocol eligibility criteria.

In calculating pre-treatment days of tests and measurements, the day a test or measurement is done is considered Day 0. Therefore, if a test is done on a Monday, the Monday four weeks later would be considered Day 28.

Note: All questions regarding eligibility should be directed to the PrECOG Study Contact in study materials. Questions will be further discussed with the medical leads for the trial as deemed appropriate (e.g., medical monitor, study chair).

Investigator sites may use the eligibility checklist (see Appendix A: Eligibility Checklist) which will be provided as a separate study document, as documentation that eligibility criteria were verified. If used, it should be reviewed, signed, and dated prior to patient randomization by the treating physician, and all required elements of source documentation must be found in the patient record (e.g. scans, consent, pathology).

Inclusion Criteria:

1. Must be willing to sign a protocol-specific informed consent.
2. Patients must be 18 years of age or older.
3. Patients must have an ECOG Performance Status 0 or 1 (see Appendix B: ECOG Performance Status Scale).
4. Patients must have histologically or cytologically confirmed adenocarcinoma of the breast.
5. Patients must have stage IV disease or inoperable locally advanced disease.
6. Patients must have ER and/or PR-positive disease as determined by their local pathology or reference laboratory by ASCO-CAP criteria.⁵¹ Tumors must be HER-2/neu negative or equivocal by standard ICH/FISH or ICH/CISH methodologies by ASCO-CAP criteria.⁵²
7. Patients must be Aromatase Inhibitor (AI) resistant, defined as:
 - relapsed while receiving adjuvant therapy with an aromatase inhibitor (anastrozole, letrozole, or exemestane) or,
 - progressive disease while receiving an aromatase inhibitor for metastatic disease.

Note: Patients may have received an endocrine agent (e.g., Tamoxifen) between the time of progression on an AI and registration.

8. Patients who have received one prior cycle (dose on day 1 and day 15) of fulvestrant within 28 days of randomization are eligible so long as they meet other eligibility criteria.
 - patients previously treated with two or more prior cycles of fulvestrant are not eligible.

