13. Patients with basal cell or squamous cell carcinoma of the skin or carcinoma *in situ* of the cervix within the past five years must have been treated with curative intent. Patients with a history of prior malignancy are eligible provided they were treated with curative intent and have been free of disease for >3 years.

Exclusion Criteria:

1. Patients who have had any major surgery or significant traumatic injury within 4 weeks of randomization, or have not recovered from the side effects of any major surgery (defined as requiring general anesthesia) or patients that may require major surgery during the course of the study are not eligible. (Placement of vascular access device will not be considered major surgery.)
2. Patients may not be receiving any other investigational agents or have received any investigational agent within 4 weeks of randomization.
3. Patients must not be receiving any concomitant anticancer treatment or have received anticancer treatment within 4 weeks of randomization (including chemotherapy, radiation therapy, antibody based therapy, etc.), with the following exceptions:
 - Bisphosphonates, Zometa or Xgeva for bone metastases
 - Hormonal therapy (e.g., AI, Tamoxifen)
 - a GnRH analog is permitted if the patient had progressive disease on a GnRH analog plus a SERM or an AI; the GnRH analog may continue but the SERM or AI must be discontinued.
4. Patients must not have received prior treatment with an mTOR inhibitor (sirolimus, temsirolimus, everolimus).
5. Patients must not be receiving chronic, systemic treatment with corticosteroids or another immunosuppressive agent greater than or equal to 5 mg prednisone or its equivalent daily. Topical or inhaled corticosteroids are allowed.
6. Patients must not receive immunization with attenuated live vaccines within one week of randomization or during the study period. Close contact with those who have received attenuated live vaccines should be avoided during treatment with everolimus. Examples of live vaccines include intranasal influenza, measles, mumps, rubella, oral polio, BCG, yellow fever, varicella and TY21a typhoid vaccines.
7. Patients must not have current or a prior history of brain metastases or leptomeningeal disease. Patients must not have rapidly progressive, life-threatening metastases. This includes patients with extensive hepatic involvement (>50% of the liver involved) and symptomatic lymphangitic metastases.

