## **7.8. Safety Analysis**

### **7.8.1. Adverse Events**

Adverse events (AEs) will be graded using CTC Version 4, coded using MedDRA dictionary version 16.0, and flagged as treatment emergent if start date of the adverse event is on or after Cycle 1 Day 1 dosing. For adverse events with partial start date (i.e., with only month and year are recorded), the following imputation rule will be applied: 15th of the month or first dose date, whichever comes later.

All AEs and treatment-related AEs will be summarized for all treated subjects by toxicity grade and by treatment arm.

AEs with relationship reported as 'Definite', 'probable' and 'possible' are considered study drug related. AEs with relationship reported 'not likely' and 'not related' are considered not study drug-related. AEs with missing relationship will be considered study drug related.

The following by subject data listings will be prepared: subjects with serious adverse events, subjects with Grade 5 adverse events, and subjects with second primary cancer.

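### SAP 7.4 does not cap imputed diagnosis and recurrence/progression dates at informed consent, so a partial date in the month or year of consent can give a negative time since the event

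*SAP*

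**What the plan says.** SAP 7.4 lists two durations among the baseline characteristics: time since diagnosis, and "Time since recurrence / progression (months) as continuous variable". Both are counted back from consent by the same formula. For the second it reads: "Time since recurrence / progression = (date of informed consent – date of recurrence / progression + 1)/30.4375".

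The imputation rules cover both dates: "Partial dates for date of diagnosis or for date of recurrence / progression will be imputed as follows". There are two of them:

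- "if the day is missing, it will be imputed it to be 15th of the month"
- "if the day and the month are missing, it will be imputed to 30-JUN"

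Neither rule mentions the consent date, and the SAP does not say what to do with a negative result. SAP 7.8.1 does bound its imputation of partial adverse event start dates: they go to the 15th "of the month or first dose date, whichever comes later".

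Under SAP 7.1, continuous variables are reported with mean, standard deviation, median, minimum and maximum. SAP 7.4 gives the summary by arm and overall, for randomized subjects and for the Evaluable for Efficacy population. It is Table 5 in the list of outputs requested for publication (SAP Appendix 1).

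**The concern.** A time since an event that brought the patient into the trial should not be negative. An imputed date that falls after consent makes it so, and the negative value is created by the rule rather than by the data.

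The entry criteria leave room for this. Protocol 3.1 admits patients with relapse on an adjuvant aromatase inhibitor, or with "progressive disease while receiving an aromatase inhibitor for metastatic disease", and states no minimum interval between that event and consent. Hormonal therapy is exempt from the four-week exclusion of prior anticancer treatment, so a progression shortly before consent is possible.

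What is at stake is the credibility of a published baseline table. One affected patient is enough to print a negative minimum. The bound in SAP 7.8.1 suggests that its absence from 7.4 is an oversight.

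**Working it through.** **Inputs.** The formula and the two imputation rules are from SAP 7.4. The 65 patients per arm are the figure assumed in Protocol 9.2 (130 patients randomized 1:1). The plan gives no figure for this variable to reproduce. Its two worked examples (July 1990 becomes 15 July 1990; 1976 becomes 30 June 1976) follow from its rules.

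**When the value is negative.** Let C be the consent date and R the imputed date, in days. Then T = (C - R + 1)/30.4375 months. Because of the +1, T is zero when R is one day after C, and negative when R is two or more days after C.

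**Day missing (R = 15th of the recorded month).**
- Event and consent in the same month: T is negative for consent on days 1 to 13 and zero on day 14.
- Lowest value, consent on day 1: (1 - 15 + 1)/30.4375 = -13/30.4375 = -0.43 months.
- Share of consent days in that month giving a negative value: 13/31 = 42%, 13/30 = 43%, 13/28 = 46%.
- Consent in the following month: T is at least 15/30.4375 = 0.49 months (15 February to 1 March), so never negative.

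**Day and month missing (R = 30 June of the recorded year).**
- Event and consent in the same year: T is negative for consent from 1 January to 28 June (179/365 = 49% of days) and zero on 29 June.
- Lowest value, consent on 1 January of a 365-day year: (-180 + 1)/30.4375 = -179/30.4375 = -5.88 months. In a leap year it is -180/30.4375 = -5.91.
- Consent in the following year: T is at least (185 + 1)/30.4375 = 6.11 months, so never negative.

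**Dependence on the true gap.** Assume that the date is already partial and that consent dates are spread evenly over a 365-day year. The share of negative values is then:

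| True gap, event to consent | Day missing | Year only |
|---|---|---|
| 0 days | 43% | 49% |
| 7 days | 20% | 47% |
| 14 days | 0% | 45% |
| 28 days | 0% | 41% |
| 60 days | 0% | 33% |

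These are conditional on a partial date. They are not shares of patients.

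**Effect on an arm mean, 65 patients.** In the worst case the true event is on the day of consent, with T = 1/30.4375 = 0.03 months.
- One missing-day patient: (0.03 + 0.43)/65 = 0.007 months.
- One year-only patient: (0.03 + 5.88)/65 = 0.09 months.

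**With a cap at consent.** The smallest value from an imputed date becomes 1/30.4375 = 0.03 months. Example: recurrence recorded as May 2014 and consent on 3 May 2014 gives (3 - 15 + 1)/30.4375 = -0.36 months uncapped and 0.03 months capped.

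**The case against.** A reader might infer that the variable comes out negative for recently progressed patients in general. The documents do not support that. The rule acts only on partial dates; complete dates are used as recorded. A patient with a missing day and a true gap of 14 days or more cannot be affected.

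Nor do the documents show that the date usually lies in the month or year of consent. SAP 7.4 does not say whether it is the progression on the aromatase inhibitor or an earlier recurrence. Protocol 3.1 allows another endocrine agent between that progression and registration, and one prior chemotherapy regimen for metastatic disease, so gaps of months or more are permitted.

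The year-only case needs a progression in the consent year with neither day nor month recorded. That is probably uncommon, since the eligibility checklist asks for documentation in the patient record. The SAP's examples, from 1976 and 1990, suggest that remote dates were in mind.

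For date of diagnosis the route is narrower still. A patient must have relapsed or progressed on an aromatase inhibitor after diagnosis, so a diagnosis in the month of consent is hardly possible; a year-only diagnosis in the consent year is conceivable.

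A reader might also infer that the rule harms a variable that matters to the analysis. It does not: neither duration is a stratification factor (SAP 7.3.5), and neither enters the response or time-to-event analyses (SAP 7.7). The median is reported too and hardly moves.

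All of this limits how often the fault occurs and how much it does. None of it supplies the missing bound.

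**Conclusion.** The point holds in limited form. Followed as written, SAP 7.4 can produce a negative time since diagnosis or time since recurrence/progression. This needs a partial date in the month of consent (consent on days 1 to 13, lowest -0.43 months) or, with only the year known, in the year of consent (consent 1 January to 28 June, lowest -5.88 months in a 365-day year).

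The number of partial dates is not given, so the number of affected patients cannot be estimated. The consequence is a negative minimum and a slight shift in the mean of a descriptive row, at most about 0.09 months per affected patient with 65 in the arm. PFS, TTP, OS, response, eligibility and stratification are untouched. This is a minor correction. The conclusion rests on SAP 7.4 as written; the separate table templates were not available and might contain a bound.

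**What to change.** Add one sentence to SAP 7.4: *If an imputed date of diagnosis or recurrence/progression is later than the date of informed consent, set it to the date of informed consent.*

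This is the same kind of logical bound that SAP 7.8.1 applies to adverse event start dates. It changes only imputed dates. The cost is one sentence and one line of programming, made by SAP amendment before database lock as SAP 2.1 provides. No new data are needed and no inference changes.
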